To standardize delivery and facilitate reproducibility of the yoga intervention, we detail the content and general structure of each class (**Table 2**) which will be followed by [name], YT. Procedures to assure *fidelity* to the yoga intervention will be used similar to those employed in our other trials. Briefly, steps will include: (1) extensive yoga therapist training conducted by [name] during start-up; (2) observation of [name] administering yoga sessions for at least one full wave (12 sessions) feedback provided by [name] after review of several sessions and periodic meetings to discuss fidelity.

D7b. Yoga intervention site, schedule of sessions, and group size

The in-person group yoga sessions will be held at the Rehabilitation and Integrative Therapy Lab (RIT Lab, in Coleman Hall on the Indiana University Purdue University Indianapolis campus, School of Health and Rehabilitation Sciences. The RIT lab is less than a 10 minute walk from the RVAMC. The 12 weekly sessions will include 8 to 12 participants; a group size we found optimal during our pilot study.⁷² Based on our sample size calculation, we will conduct 15-19 groups (of 8-12 participants) to complete the yoga intervention. **Attendance will be recorded to assess adherence to yoga.**

D7c. Yoga intervention components, sequence, and progression

The 12-week yoga intervention (**Table 2**) developed and previously tested by Drs. [name] and [name] and [name] will be modified for veterans with fibromyalgia. For example, [name] will emphasize “gentle practice” of yoga exercise when veterans are challenged by fibromyalgia or other chronic illnesses. The yoga exercises will be delivered in a standardized sequence and progression, as delivered in our pilot study of veterans with stroke. The yoga poses or *asanas* will consist of a single sequence that can be performed supine, seated, on hands and knees, prone, and standing. Similar to other rehabilitation interventions, our yoga intervention will progressively become more challenging for participants over the 12 weeks.

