cognitive behavioral relaxation techniques and found a 13.6% reduction in FIQR scores. From these studies, we estimate the difference between the yoga and structured exercise group is 17%. A between-group treatment difference of 14% reduction in symptoms represents a minimum clinically meaningful intervention effect.¹¹⁹ To be conservative, we will assume a 14% difference between treatment groups. The absolute score difference at 3 months is estimated to be approximately 7 points (6.79, 14% of 48.3). Assuming a common standard deviation of 17.6 and using a two-sample t-test, we will need 107 evaluable subjects in each arm to detect such a difference with >80% power and 5% Type I standard error rate.

We recognize the correlation of outcomes from subjects within the same yoga or exercise class may reduce the effective sample size compared to the same sample with independent observations. This possible “clustering effect” seen in group delivered interventions has implications for power. We have no preliminary data to estimate the intra-cluster correlation (ICC) for participants within the same group. However, based on similarly designed published studies, we expect the ICC to be relatively small and balanced across the two treatment arms since the cluster sizes will be similar.¹²⁰ Conservatively, we assume an ICC of 0.02 for both treatment groups. With 8 subjects per treatment group/class or cluster, the design effect is $1 + (8-1) \times 0.02 = 1.14$. Therefore, we will inflate our sample size by 14% to accommodate the potential clustering effects. We then need 122 evaluable subjects in each arm. With a conservative 20% attrition, we will then need $(122 \times 2) / 0.80 = 306$ subjects (153 in each arm).

D9b. Data analysis: Baseline characteristics of POYSE sample

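### D9a misstates its target difference (14% of 48.3 is 6.76, not 6.79) and leaves the class size of 8 undefined; 306 patients give about 80% power, not clearly more

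*Combined protocol and SAP*

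**What the plan says.** All references are to the combined protocol and SAP.

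- **Difference (D9a):** "The absolute score difference at 3 months is estimated to be approximately 7 points (6.79, 14% of 48.3").
- **Unclustered size (D9a):** "Assuming a common standard deviation of 17.6 and using a two-sample t-test, we will need 107 evaluable subjects in each arm". The same sentence claims power above 80% at a type I error rate of 5%. Sidedness is not stated.
- **Clustering (D9a):** "Conservatively, we assume an ICC of 0.02 for both treatment groups". Then "With 8 subjects per treatment group/class or cluster, the design effect is" 1.14, and "We then need 122 evaluable subjects in each arm". Twenty percent attrition is added after that, giving 306 (153 per arm).
- **Class size (D7a, D7b):** yoga classes hold 8 to 12, and D7b adds "we will conduct 15-19 groups (of 8-12 participants) to complete the yoga intervention". For the exercise arm I found no number; D9a says only that cluster sizes will be similar in the two arms.
- **Related statements:** D9f expects 8% to 12% dropout and calls 20% conservative. D9c plans a baseline-adjusted repeated-measures ANCOVA, which it describes as more powerful than a t-test when baseline and outcome are positively correlated. D13 lists ample power as a strength of the trial.

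**The concern.** Two inputs to the sample size do not stand as printed.

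The target difference is a wrong product. The error is 0.03 points, but the calculation has so little slack that it decides whether 107 per arm is above or below 80%.

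The class size of 8 is the bottom of the planned 8-12 range if it means enrolled patients, and about the middle of it if it means patients still evaluable after 20% attrition. D9a does not say which. The design effect rises with class size, so the reader cannot tell whether 1.14 represents the planned classes or the smallest ones permitted, nor what the exercise arm contributes.

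What is at stake is how accurately power is stated. D9a claims more than 80% and D13 calls the power ample; the reader should be able to see how much margin lies behind those words.

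**Working it through.** **Inputs.** From D9a: baseline mean 48.3, 14% reduction, SD 17.6, alpha 0.05, ICC 0.02, 8 per class, 20% attrition, 153 per arm. From D7b: 8-12 per yoga class, 15-19 groups. From D9f: 8-12% expected dropout. Assumed: a two-sided test (it reproduces 107) and the same class sizes in both arms. Power is from the noncentral t distribution with individual-level degrees of freedom, as in the plan's own calculation.

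**1. The plan's figure reproduces.** With a difference of 6.79, 107 per arm gives 80.2% power and 106 does not reach 80%. Design effect: 1 + (8 - 1) × 0.02 = 1.14. 107 × 1.14 = 121.98, so 122 per arm. 244 / 0.80 = 305, or 152.5 per arm, rounded up to 153 per arm = 306.

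**2. The difference.** 0.14 × 48.3 = 6.762. Power of the two-sample t-test:

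| Difference | 107 per arm | Smallest n per arm for 80% |
|---|---|---|
| 6.79 (printed) | 80.2% | 107 |
| 6.762 (correct product) | 79.9% | 108 |
| 7 (the rounded value) | 82.5% | 101 |

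**3. Class sizes implied by D7b.** 153 / 19 = 8.05 and 153 / 15 = 10.2 enrolled on average. After 20% attrition these are 6.44 and 8.16 evaluable. A class of 10 leaves 10 × 0.80 = 8.0, which is the plan's own figure. A class of 12 leaves 9.6, but filling every class to 12 needs 153 / 12 = 12.75 groups, outside 15-19.

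**4. Power of 306 with attrition applied to arms and classes alike.** Evaluable per arm: 153 × 0.80 = 122.4. With m evaluable per class, design effect = 1 + (m - 1) × 0.02 and effective n = 122.4 / design effect. Difference 6.762:

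| Enrolled per class | Evaluable m | Design effect | Effective n per arm | Power |
|---|---|---|---|---|
| 8 | 6.4 | 1.108 | 110.5 | 81.1% |
| 10 | 8.0 | 1.140 | 107.4 | 80.0% |
| 10.2 | 8.16 | 1.143 | 107.1 | 79.9% |
| 12 | 9.6 | 1.172 | 104.4 | 78.9% |

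Rounding up to 153 per arm supplies 122.4 evaluable rather than 121.98, which is why 8 evaluable per class comes back to 80.0% although 107 alone gives 79.9%.

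**5. At the dropout D9f expects.** The same steps with 8% and 12% loss:

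| Dropout | 8 enrolled per class | 12 enrolled per class |
|---|---|---|
| 8% (140.76 evaluable per arm) | 85.6% | 83.4% |
| 12% (134.64 evaluable per arm) | 84.3% | 82.0% |

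**The case against.** The strongest reply is that this is rounding. The slip is 0.03 points on a 0-100 scale, in a sentence that speaks of approximately 7 points, and at 7 points 107 per arm gives 82.5%. The 20% attrition is deliberately pessimistic, and the ANCOVA in D9c should do better than a t-test. Most of this stands, and it is why the point is small. It does not rescue the printed text: 107 is the size that belongs to 6.79, not to 7, and 6.79 is given as a product that it does not equal. The ANCOVA gain cannot be credited to the stated figure, because no baseline correlation is given.

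A reader might go further and infer that D9a used the most favourable class size, that 306 gives only about 77-79% power at 10-12 per class, and that some 316-326 patients were needed. The documents do not support this. Those figures take 20% attrition out of the arm but leave the classes full. D9a applies the design effect to evaluable patients and adds attrition afterwards, so the consistent class size is the evaluable one. On 15-19 groups that is 6.4-8.2, which puts 8 near the top of the implied range of means. If all classes did retain 12, nobody would have dropped out; 153 per arm would then be evaluable and power would be 85.8%. Nor does D9a call the class size conservative: it uses that word of the 14% difference, the ICC and the attrition.

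**Conclusion.** The point holds as a correction to the stated figures, not as a failure of the sample size. The printed difference is wrong; with the right one, 107 per arm gives 79.9% and 108 are needed. The class size of 8 is undefined, and the exercise class size is not given as a number. With 306 randomised, 20% attrition and ICC 0.02, power by t-test is about 80%: 81.1% to 79.9% over the mean class sizes implied by 15-19 groups, and 78.9% if every class enrolled the permitted maximum of 12. The shortfall against 80% is therefore about 0.1 percentage point within the planned number of groups, and about 1 point at the extreme.

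This rests on a two-sided test, similar classes in both arms, individual-level degrees of freedom and the plan's ICC. D9a has no preliminary data for the ICC, and it matters more than class size: at the printed 6.79 with 122 evaluable per arm and 8 per class, an assumed ICC of 0.01 gives 82.7% and 0.05 gives 73.2%.

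**What to change.** In D9a:

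1. Replace 6.79 with 6.76.
2. State that 8 is the evaluable class size, corresponding to about 10 enrolled less 20% attrition, and give the planned class size for the exercise arm.
3. In place of more than 80%, state that with 306 randomised, 20% attrition and ICC 0.02, power by two-sided t-test is about 80%: 81% at 8 enrolled per class, 79.9% at 10.2 and 79% at 12, assuming similar classes in both arms.
4. If wanted, report separately the power at the expected 8-12% dropout (about 82-86% for 8-12 enrolled per class) and any gain from baseline adjustment, with the correlation assumed for it.

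The description of power in D13 should be brought into line. The cost is a slightly less favourable stated power; no patients are added, and neither the design nor the analysis changes.

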Epidemiologic studies^{28,29} have assessed fibromyalgia prevalence and other symptom-based conditions among Gulf War Veterans. Buskila et al.²⁹ found 17% of Gulf War Veterans with soft tissue rheumatism also had concomitant fibromyalgia; representing a much higher prevalence than seen in previous studies of military populations. In the Iowa Persian Gulf Study, fibromyalgia symptoms were reported by 18%-24% of Gulf War Veterans relative to 9%-13% of non-deployed personnel.²⁸ Eisen et al³ found that a diagnosis of fibromyalgia was twice as prevalent in deployed vs. non-deployed Gulf War Veterans.

Another study examined health care utilization and found that Gulf War Veterans were at an increased risk of postwar hospitalization for fibromyalgia.³⁰ The prevalence in Iraq and Afghanistan War Veterans has not yet been reported. Beyond these epidemiologic studies focused on Gulf War veterans with fibromyalgia, research in veteran populations is limited. A potential explanation for this paucity of research is the perception that fibromyalgia is relatively uncommon in men. Although fibromyalgia in men is largely unexplored, one study of men with fibromyalgia found they had more severe symptoms, worse physical function, and lower quality of life³¹ than women with fibromyalgia. In this context, studies that focus on relieving the suffering of veterans with fibromyalgia are imperative.

B4. Medications are the most common treatments for fibromyalgia, but have modest benefits

Medications for fibromyalgia are largely targeted at its symptoms, especially depression, sleep disturbance and muscle pain. Tricyclic anti-depressants, selective serotonin reuptake inhibitors (SSRI), skeletal muscle relaxants, analgesics, dual reuptake inhibitors (SNRIs), anticonvulsants, and dopamine agonists have been used with some success.¹ In 2007, the Federal Drug Administration approved Lyrica (pregabalin) as the first medication to treat fibromyalgia. Cymbalta (duloxetine) was approved in 2008; and Savella (milnacipran) was approved in 2009.

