The yoga intervention is designed to improve functioning, pain, fatigue, sleep problems, and psychological distress common to patients with fibromyalgia. The intervention will include exercises or physical activity that includes postures (*asanas*), diaphragmatic breathing (*pranayama*), relaxation/meditation practices (*dhyanas*), and discussions sessions between [name] and group

D6. RANDOMIZATION

Stratified and blocked randomization will be performed. After providing written-informed consent and completing their baseline interview, participants will be randomized to one of two arms: 1) yoga-based intervention (YOGA); or 2) a structured exercise program (SEP). ***The randomization process will be directed by [name] (statistician) using statistical software with a random-number generator to create a list of group assignments before study recruitment begins.***

Randomization will be stratified by sex (men vs. women) and study recruitment site (VAMC vs. CBOC). Within strata, randomization with block sizes of 4 or 6 will be executed to ensure balance. Once an eligible participant has been screened, has signed informed consent, and has completed the baseline measures the research assistant ([name]) or project coordinator ([name]) will submit a request to randomize the eligible participant. The randomization program locates the first unassigned record in the randomization list and assigns the participant to the group designated in that record. The participant identifier and date are written to the record. To ensure allocation concealment, only [name] and [name] will have access to the randomization table, but will not conduct outcome assessments. [name] will remain blinded to group assignment. No one will be allowed access to the folder of the randomization assignment until all baseline measures have been completed.

participants to exchange “lessons learned.” Patients will be given yoga mats and eye pillows and will have access to yoga blankets, yoga straps, and bolsters for doing yoga poses.

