Health Care Utilization and Costs: will be assessed at the end of the 9 month study period for each patient using data available in CPRS. This will include all outpatient, rehabilitation, and emergency room visits, inpatient days, x-ray and lab tests, medical and surgical consultations, and medications.

D9. STATISTICAL CONSIDERATIONS

POYSE will involve a 2-arm, parallel group, randomized comparative effectiveness trial. Since participants cannot be blinded to treatment assignment, observed outcomes (if positive) could be affected by expectation bias. To account for this potential bias, we will assess treatment expectations at baseline and account for expectations in our analyses. We will randomize at the patient rather than the provider level for two reasons: (1) randomization at patient level saves sample size; and (2) patients from the same provider in the two arms will adjust for “provider effect.” Contamination will also be low because there is relatively minimal involvement required of VA providers in POYSE. In addition, randomization will be stratified by sex (women or men) and **study recruitment site (VAMC or CBOC)** to avoid potential imbalance of these factors between the two arms. [name], PhD (statistician) will create a randomization chart to randomize patients in **blocks of 4 or 6**.

D9a. Sample size

Our sample size is calculated based on estimated differences of intervention effects between two arms on the primary outcome; Fibromyalgia Impact Questionnaire Revised (FIQR) total score at 3 months.

The FIQR total score is a continuous measure: a 0-100 scale and reflects the average of three domains: function, overall impact, and symptoms. In a recently published yoga trial for patients with fibromyalgia, Carson et al.⁶¹ found a pre-treatment FIQR score of 48.3 (standard deviation = 17.5).

Post-treatment scores were reduced by 31% (FIQR = 35.5, SD = 17.6, effect size = 0.72) from the yoga intervention. In an earlier trial, Mannerkopi et al.¹¹⁸ tested an intervention combining pool exercises with

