We will examine baseline characteristics (socio-demographic variables, medical and psychiatric comorbidity, duration of fibromyalgia, and current and prior pain treatments) of the POYSE sample. To evaluate the representativeness of study enrollees among all eligible patients, we will compare the enrollees and those who decline enrollment on their demographic characteristics. If there are systematic differences, these will be considered in the interpretation of the results of subsequent analyses. We will also examine differences in baseline characteristics between patients who remain in the study and those who dropout. Two-factor ANOVA models which include dropout status, treatment group (YOGA vs. SEP) and their interaction will be used for continuous variables. Logistic regression models with the same terms will be used for dichotomous variables.

D9c. Main analysis of the primary outcome (FIQR total score)

Our main analysis will employ a repeated measurement analysis of covariance (ANCOVA) model which is more powerful than two-sample t-test when the baseline outcome measurement is positively correlated with post baseline outcome.¹²¹ We plan an intent-to-treat analysis approach with the primary endpoint at 3 months and evaluation of “early” response at 1 month and “sustained” response at 3 and 6 months post-intervention. We will summarize this primary outcome at each time point (baseline, 1, 3, 6, and 9 months) for both arms. The difference between time points will be compared.

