Since the primary outcome (FIQR total score) is measured repeatedly at baseline, 1, 3, 6, and 9 months, we will fit a repeated measurement analysis of covariance (ANCOVA) model with the four post baseline (1, 3, 6, and 9 months) FIQR total score as the response variables. The main predictors will be group (treatment arm), time (categorical), and their interaction. The model will be adjusted for baseline FIQR score. A random intercept will be used to adjust for the patient effect and to accommodate the correlation among the repeated measurements from the same patients. Another random intercept will be used to adjust for the potential clustering effect for patients in a specific yoga or exercise group. The primary analysis will evaluate the difference in FIQR score between the two treatment arms at 3-months (the primary end point) using appropriate contrast in this model. The sustained effect of intervention will be evaluated using appropriate contrast for the difference in FIQR change from 3-month to 6-month in this model.

D9d. Secondary analysis of primary outcome

For the FIQR total score, we will also define the patients with more than 30% reduction as “responders.” We will then compare the probability of responders between treatment arms using a generalized linear mixed model with a logit link. The responding status of each patient at **1, 3, 6, and 9 months** will be used as the outcome variables. Main predictors are group (treatment arm), time (1, 3, 6, and 9 months), and their interaction. A significant coefficient of group indicates a significant odds ratio of being a responder between the two arms at each time point. Each of the three domains of the FIQR score will be analyzed in the similar way to the total score.

D9e. Analysis of secondary outcomes

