Since POYSE is not specifically powered for the secondary outcome, these results should be interpreted cautiously unless they are highly significant ($p < .001$). Pain severity as assessed by the Brief Pain Inventory will be analyzed using a repeated measurement ANCOVA model in the same way as the FIQR total score. BPI measurement at 1, 3, 6, and 9 months will be used as the response variable. Main predictors will be intervention group, time (categorical), and their interaction adjusted for the baseline BPI score. A random intercept of subject effect will be used to accommodate correlation within subject. Another random intercept of either a specific yoga or exercise group will be used to accommodate correlation within group (clustering effect for group delivered intervention).

Psychological symptoms: PHQ-9 score, GAD-7 will be analyzed using a repeated measurement ANCOVA model in the same way as the FIQR total score with repeated outcomes at 1, 3, 6, and 9 months as the response variables, the same set of main predictors and adjusted for baseline outcome measurement. The PTSD screening status will be analyzed using a generalized linear mixed model with a logit link. The main predictors will be intervention group, time (categorical) and their interaction adjusted for baseline PTSD screening status. PTSD severity from PTSD checklist for military will be analyzed similarly.

Other secondary outcome measures: The analytical strategy for other outcomes will be similar to the FIQR total score. These outcomes include SF-36, MFI, MOS Sleep Scale, Pain Catastrophizing Scale, Arthritis Self-Efficacy Scale, and PGIC.

We will employ several secondary analyses to assess the effectiveness of the treatment arms compared to each other in improving:

- Individual fibromyalgia symptoms (pain, fatigue, sleep quality, function)
- Health-related quality of life
- Patient global impression of change
- Pain beliefs and self-efficacy

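### The primary FIQR model omits the two randomisation strata, sex and recruitment site; adding them is a small, nearly free improvement

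*Combined protocol and SAP*

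**What the plan says.** - **Randomisation (D6).** "Randomization will be stratified by sex (men vs. women) and study recruitment site (VAMC vs. CBOC"), in blocks of 4 or 6 within strata.
- **Purpose (opening of D9).** The strata are repeated there, and the aim is "to avoid potential imbalance of these factors between the two arms".
- **Primary model (D9c).** The response is FIQR total score at 1, 3, 6 and 9 months. The fixed terms are arm, categorical time and their interaction. Then: "The model will be adjusted for baseline FIQR score". There is a random intercept for patient, and "Another random intercept will be used to adjust for the potential clustering effect for patients in a specific yoga or exercise group". The primary test is the 3-month contrast between arms.
- **Reason for ANCOVA (D9c).** It was chosen as a method "which is more powerful than two-sample t-test when the baseline outcome measurement is positively correlated with post baseline outcome".
- **Other outcomes.** D9d handles the three FIQR domains like the total score. D9e has pain severity "analyzed using a repeated measurement ANCOVA model in the same way as the FIQR total score" and treats most other scales alike. Responder status (D9d) and PTSD screening status (D9e) use a "generalized linear mixed model with a logit link".

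Sex and recruitment site appear in none of these models, and no reason is given for leaving them out. The adjustments mentioned elsewhere concern expectations (D9), co-interventions (D7j), and comorbidities, age and prior cost (the cost model in D9i). None of them is a stratum.

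**The concern.** When allocation is balanced within strata that predict the outcome, the arm difference varies less from trial to trial than it would under simple randomisation. A model without the strata leaves their contribution in the residual variance, so it reports a standard error that is too large for the design. Confidence intervals are then a little wide and the test rejects a little less often than it should.

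The documents give modest grounds for thinking the factors could matter. Section B3 says that "one study of men with fibromyalgia found they had more severe symptoms, worse physical function". D3 puts the community clinics about an hour's drive from Indianapolis, and D7b and D7f place the sessions of both arms at one campus laboratory there. The class random intercept does not stand in for recruitment site, because nothing says that classes are formed by site.

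**Working it through.** **1. The plan's sample size (D9a).** Inputs: difference 6.79, SD 17.6, power 80%, two-sided alpha 5% (sidedness is not stated; two-sided is assumed).
- The exact two-sample t-test needs 106.4, so 107 per arm (power 80.2% at 107).
- 107 × 1.14 = 121.98, so 122 per arm.
- 122 / 0.80 = 152.5, so 153 per arm and 306 in total.

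These figures reproduce. They come from an unadjusted t-test, so adding strata to the model does not change them.

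**2. Setting up the comparison.** Let R2 be the share of patient-level variance, after baseline FIQR, that sex and site explain. Let rho be the baseline to 3-month correlation. Neither is in the documents, so both are assumed.
- Residual SD after baseline at rho 0.5: 17.6 × sqrt(1 − 0.25) = 15.24.
- Model SE without the strata, 122 per arm: SE0 = 15.24 × sqrt(2 × 1.14 / 122) = 2.084.
- With ICC 0.02 and classes of 8, the variance factor is (1 − 0.02) + 8 × 0.02 = 1.14. Strata that explain patient-level variance reduce only the first part, giving 1.14 − R2.
- True SE under stratified allocation: SE1 = 15.24 × sqrt(2 × (1.14 − R2) / 122).

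**3. Formulas.** SE overstatement = SE0/SE1 − 1 = sqrt(1.14/(1.14 − R2)) − 1. Type I error without the strata = 2 × [1 − Φ(1.96 × SE0/SE1)]. Power without the strata = Φ((6.79 − 1.96 × SE0)/SE1). Power with them = Φ(6.79/SE1 − 1.96).

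**4. Results at rho 0.5.**

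| R2 | SE1 | SE too large by | Type I error | Power without | Power with | Loss (points) |
|---|---|---|---|---|---|---|
| 0 | 2.084 | 0 | 5.0% | 90.3% | 90.3% | 0 |
| 1% | 2.074 | 0.4% | 4.9% | 90.4% | 90.5% | 0.15 |
| 2% | 2.065 | 0.9% | 4.8% | 90.5% | 90.8% | 0.29 |
| 5% | 2.037 | 2.3% | 4.5% | 90.8% | 91.5% | 0.71 |
| 10% | 1.990 | 4.7% | 4.0% | 91.3% | 92.7% | 1.37 |

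Across R2 of 1% to 10%, the same formulas give a loss of 0.2 to 2.0 points at rho 0.3 (SE0 2.295) and of 0.05 to 0.4 points at rho 0.7 (SE0 1.718).

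**5. Which rows are plausible.** With a proportion p of women, the sex difference needed for sex alone to give R2 is sqrt(R2/(p(1 − p))) × 15.24. D4 reports 12.5% women in an earlier trial and expects more here, so p is assumed to be 0.15 to 0.20. The difference needed after baseline adjustment is 3.8 to 4.3 FIQR points for 1%, 5.4 to 6.0 for 2%, 8.5 to 9.5 for 5% and 12.0 to 13.5 for 10%. The last two exceed the 6.79-point treatment effect.

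**6. Simulation of the direction.** Stratified blocks of 4 or 6 were simulated with 214 patients, one time point, 20% women and 30% community-clinic patients (both assumed), and 6,000 runs per setting. With 5-point effects of each factor, type I error without and with the strata was 4.6% and 4.8%. With 8-point effects it was 4.1% and 5.1%. Simulation error is about 0.3 points, so the first pair does not separate the models. The check has no baseline covariate, classes or repeated visits, so it supports the direction but not the sizes in step 4.

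**The case against.** The best case against is that nothing of consequence is lost. Stratification was adopted to prevent imbalance, and the design achieves that without any model term. The plan claims extra power only from baseline FIQR. Nothing in the documents shows that sex or site predicts FIQR once baseline is in the model: the study of men concerns severity, much of which baseline FIQR will absorb, and a drive time is not evidence about symptoms. Power under the adjusted model is already about 90% at rho 0.5, against a target above 80%. All of this stands, and it keeps the severity low. It does not remove the mismatch between how patients are allocated and how they are analysed.

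A reader might infer more than the documents support:
- **Bias or inflated type I error.** Neither follows. In a linear model with strata balanced by design, the estimate stays unbiased and the error moves in the conservative direction.
- **Loss of the precision that stratification provides.** The design has already reduced the true variability of the estimate. Only the reported standard error fails to show it.
- **A material loss of power.** That needs R2 of 5% to 10%, which step 5 makes unlikely.
- **A broken promise.** The plan never says that the strata will be in the model, so this is a missed improvement and not a contradiction.

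**Conclusion.** The point holds as a low-severity improvement. D9c and the continuous-outcome models built on it leave out both randomisation strata. The effect is a slightly conservative analysis: a standard error about 0.4% to 0.9% too large and a power loss of about 0.15 to 0.3 points at R2 of 1% to 2% and rho 0.5. The loss would be about 0.7 points at R2 of 5% and 1.4 at 10%, and zero if neither factor is prognostic after baseline. These sizes rest on assumed R2 and rho, on the plan's ICC of 0.02 with classes of 8, and on strata that explain patient-level rather than class-level variance. The change is worth making because it costs almost nothing and settles in advance whether the strata are adjusted for. The trial's conclusions are unlikely to depend on it.

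**What to change.** Add sex (men/women) and recruitment site (VAMC/CBOC) as fixed effects to the D9c linear mixed model, and to the continuous-outcome models in D9d and D9e. If they are to stay out, state why.

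Optionally add the interaction of each factor with time, so that the 3-month contrast is adjusted for visit-specific effects. Main effects alone hold the sex and site effects constant from 1 to 9 months, whereas any effect of travel to sessions would be expected mainly during the 3-month intervention.

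Decide separately, and state, whether the logit-link models for responder status and PTSD screening include the strata, because added covariates change the conditional odds ratio being estimated.

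The cost is analysis-plan wording and two degrees of freedom. Time interactions over four visits add 2 × 3 = 6 more. Both variables are known at randomisation, and the target of 306 is unchanged.
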